4.4 TREATMENT FOR CHOROIDAL NEOVASCULARIZATION WITH RANIBIZUMAB

4.4.1 Ranibizumab

4.4.1.1 Formulation for Sites in the United States

Note: German sites will use commercially available Lucentis.

At U.S. sites, ranibizumab will be supplied by the Sponsor. For information on the formulation and handling of ranibizumab, see the *pharmacy binder* for ranibizumab.

Dosage, Administration, and Storage

At the discretion of the investigator, enrolled patients who are receiving study treatment and are diagnosed with CNV in either eye may receive treatment with 0.5 mg ranibizumab. For U.S. sites, the drug will be open-label ranibizumab for investigational use only supplied by Genentech. The ranibizumab injection in the United States will be performed using the techniques as discussed in *the pharmacy binder*. Sites in Germany will use commercially available ranibizumab (Lucentis) and consult with the region-specific Lucentis Prescribing Information for the recommended dose, frequency, and administration of treatment.

NOTE: If treatment with ranibizumab is to be given (to study and/or non-study eye) at the same visit as a study eye treatment with lampalizumab, the treatment with ranibizumab must be administered first. The safety assessments (including IOP check) to proceed to the study eye treatment with lampalizumab must be assessed prior to calling the IxRS for the study treatment kit assignment. Individual trays and sterile prep must be separately prepared for each treatment.

Note: Sites will contact the IxRS to report the treatment with the Genentech-supplied ranibizumab and record this information on the specific eCRF page. For German sites, ranibizumab will be recorded on the concomitant medications eCRF.

*Detailed instruction for ranibizumab storage is provided in the *pharmacy binder*. Each vial will be labeled as required by the relevant regulatory agencies.*

4.5 CONCOMITANT AND EXCLUDED THERAPIES

4.5.1 Permitted Concomitant Therapy

Permitted concomitant medications are any prescription drugs or over-the-counter preparations other than protocol-specified procedural treatments (e.g., dilating drops, fluorescein dyes, etc.) and pre- and post-injection medications (e.g., proparacaine, investigator-applied antimicrobials (if applicable) pre and post injection, etc.) used by a patient at the time of study enrollment on the Day 1 visit and through study completion or the ET visit.

Patients who use other maintenance therapies should continue their use. Patients required to use medications described in Excluded Concomitant Therapy (see Section 4.5.2) will not be eligible for enrollment or continuation in the study.

All concomitant medications should be reported to the investigator and recorded on the appropriate eCRF.

The onset of glaucoma in the study eye during a patient's study participation should be treated as clinically indicated.

Of note, the following are some common therapies that are permitted:

- Short-term use of topical corticosteroids after cataract surgery, YAG capsulotomy, or peripheral iridotomy.
- Oral corticosteroids at doses \leq 10 mg/day prednisone or equivalent
- Onset of ocular hypertension or glaucoma in the study eye during a patient's study participation should be treated as clinically indicated.
- Onset of cataract or posterior capsular opacification in either eye during the patient's study participation may be treated as clinically indicated. Dose-interruption criteria (see *Table 2*) may apply with cataract surgery.
- At the discretion of the investigator, enrolled patients who are receiving study treatment and are diagnosed with CNV may be treated with ranibizumab if they are diagnosed in either eye with CNV.

NOTE: If treatment with ranibizumab is to be given (to study and/or non-study eye) at the same visit as a study eye treatment with lampalizumab, the treatment with ranibizumab must be administered first. The safety assessments (including IOP check) required to proceed to the study eye treatment with lampalizumab must be assessed prior to calling IxRS for the study drug kit assignment. Individual trays and sterile prep must be separately prepared for each treatment.

4.5.2 Excluded Concomitant Therapy

At the discretion of the investigator, patients may continue to receive all medications and standard treatments administered for other conditions. The following medications/treatments are prohibited from use during the patient's participation in the study:

- Systemic anti-VEGF agents
- ITV anti-VEGF agents (other than ranibizumab) in either eye
- ITV, subtenon, or chronic topical (ocular) corticosteroids in the study eye
- Systemic or IV immunomodulatory therapy (e.g., azathioprine, methotrexate, mycophenolate mofetil, cyclosporine, cyclophosphamide, anti-tumor necrosis factor α agents)
- *Ocular or systemic* complement inhibitors, (e.g., eculizumab) except lampalizumab
- Treatment with Visudyne[®] in either eye
- Other experimental therapies (except *those involving* vitamin and mineral supplements)

4.5.3 Excluded Concomitant Conditions

- Medical or surgical conditions or clinical laboratory findings giving reasonable suspicion of a disease or condition that contraindicates the use of an investigational drug, or that might affect interpretation of the study results, or that may render a study patient at high risk for treatment complications; when such a condition is identified, consultation with the Medical Monitor will be required to determine a patient's eligibility to continue on the extension study

4.6 STUDY ASSESSMENTS

Please refer to the detailed schedules of assessments provided in [Appendix 1-A](#) through [Appendix 1-F](#).

Patients enrolled from Study CFD4870g will have up to 96 study visits (excluding the Day 1 visit). Patients enrolled from Study GX29455 will have up to 54 study visits (excluding the Day 1 visit). Any patient who discontinues the study prematurely (prior to the Month 96 visit for patients from Study CFD4870g and prior to the Month 54 visit for patients from Study GX29455) will have an ET visit completed \geq 30 days after his or her last study drug treatment. Study visits will be scheduled every 30 (\pm 7) days relative to the Day 1 visit.

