3.1.3 All Extension Study Patients

A patient must satisfy all eligibility criteria at Day 1 visit and will be enrolled using an interactive response system (IxRS). All patients enrolled in the extension study will have the first ITV injection of lampalizumab administered by the investigator at the Day 1 visit (unless dose holding is medically justified by the investigator) which is scheduled on the same day and immediately following the conclusion of the Month 18 visit for Study CFD4870g or Week 24 visit for Study GX29455. Requisite Study CFD4870g Month 18 and Study GX29455 Week 24 assessment data will be extracted and incorporated into extension study Day 1 datasets.

All patients who enroll in Study GX28198 will have scheduled monthly visits with monthly study-drug treatment for the duration of their study participation (see [Table 1](#)).

Table 1 Dosing Schema

Treatment	Day 1 ^a	Monthly Lampalizumab Dosing Visit Month 1 through Visit Month 95 ^b or Visit Month 1 through Visit Month 53 ^c	ET ^e or Final visit Month 96 ^d or Month 54 ^d
Lampalizumab 10-mg ITV injections	x	x	

ET = early termination; ITV =intravitreal.

- ^a Day 1 visit will occur at the conclusion of the Month 18 visit for Study CFD4870g or Week 24 visit for Study GX29455; the first study drug administration for the extension study is at the Day 1 visit.
- ^b Patients enrolled from Study CFD4870g in the monthly treatment arm continue to receive monthly lampalizumab treatment (Months 1–95) without change; patients in the every-other-month treatment arm were crossed over to the monthly treatment arm and are receiving monthly lampalizumab treatment for the remainder of their 95-month study treatment period.
- ^c Patients enrolled from Study GX29455 will receive monthly treatment (visit Months 1–53) with lampalizumab irrespective of the treatment arm (Q2W or Q4W) they were randomized to in Study GX29455.
- ^d Month 96 visit is a final study visit for patients enrolled from Study CFD4870g and Month 54 visit is the final study visit for patients enrolled from Study GX29455; no study treatment will be administered at the final visit.
- ^e *Patients may undergo an ET visit as per protocol section 4.7 through 4.9; no study treatment will be administered at this visit.*

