4.1.2.1 General Inclusion Criteria

- Willingness and ability to provide signed Informed Consent; in addition, at U.S. sites, Health Insurance Portability and Accountability Act (HIPPA) authorization, in other countries as applicable according to national laws
- Ability and willingness to undertake all scheduled visits and assessments
- For CFD4870g patients: Previous enrollment and completion (Month 18 visit) of Study CFD4870g without early treatment discontinuation (lampalizumab or sham)
- For GX29455 patients: Previous enrollment and completion (Week 24 visit) of Study GX29455 without early treatment discontinuation (lampalizumab or sham)
- For women of childbearing potential: agreement to remain abstinent (refrain from heterosexual intercourse) or use contraceptive methods that result in a failure rate of < 1% per year during the treatment period and for at least 30 days after the last dose of study drug.

A woman is considered to be of childbearing potential if she is post-menarcheal, has not reached a post-menopausal state (≥ 12 months of amenorrhea with no identified cause other than menopause), and has not undergone surgical sterilization (removal of ovaries and/or uterus).

Examples of contraceptive methods with a failure rate of < 1% per year include bilateral tubal ligation, male sterilization, established, proper use of hormonal contraceptives that inhibit ovulation, hormone-releasing intrauterine devices, and copper intrauterine devices.

The reliability of sexual abstinence should be evaluated in relation to the duration of the clinical trial and the preferred and usual lifestyle of the patient. Periodic abstinence (e.g., calendar, ovulation, symptothermal, or postovulation methods) and withdrawal are not acceptable methods of contraception.

- For men: agreement to remain abstinent (refrain from heterosexual intercourse) or use contraceptive measures and agreement to refrain from donating sperm, as defined below:

With female partners of childbearing potential, men must remain abstinent or use a condom plus an additional contraceptive method that together result in a failure rate of <1% per year during the treatment period and for at least 30 days plus 90 days (a spermatogenesis cycle) after the last dose of study drug. Men must refrain from donating sperm during this same period.

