4.6.3 Assessments during Treatment

After a patient has signed the informed consent form, the site will contact the IxRS to obtain a patient enrollment ID number assignment and to report the study drug distribution on the Day 1 visit (at conclusion of Month 18 visit in study CFD4870g or Week 24 visit in study GX29455). Patient self-administered antimicrobials in the pre- and post-injection period may be used at the investigator's discretion.

At all study visits the procedures and assessments should be performed prior to study drug administration unless otherwise indicated. All study visit assessments must be performed on the same day. *Note: see Section 3.1.3 for exception regarding delayed study treatment administration.*

The study scheduled visits should occur every 30 (± 7) days relative to the Day 1 visit date. Dosing should not occur earlier than 23 days after the previous dosing.

Please see the Study Flowcharts provided in [Appendix 1-A](#) through [Appendix 1-E](#) for the schedule of treatment period assessments.

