4.6.4 Study Completion/Early Termination Visit

For patients who withdraw early from the study (prior to the Month 96 visit for patients enrolled from CFD4870g and prior to the Month 54 visit for patients enrolled from GX29455) for any reason, these patients should complete the ET visit assessments ≥ 30 days following the last study treatment. Patients who discontinue from the study will not be allowed to re-enter the study. Please see the Study Flowcharts provided in [Appendix 1-A](#) through [Appendix 1-E](#) for the assessments to be performed at the study ET visit.

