5.3.1 Adverse Event Reporting Period

Investigators will seek information on adverse events at each patient contact. All adverse events, whether reported by the patient or noted by study personnel, will be recorded in the patient's medical record and on the Adverse Event eCRF.

At the time of enrollment, any adverse events or serious adverse events that are ongoing from Study CFD4870g or study GX29455 should be recorded on the GX29198 eCRF.

After initiation of study drug, all adverse events will be reported until the last study visit. After this period, the investigator should report any serious adverse events that are believed to be related to study drug treatment (see Section [5.6](#)).

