5.3.6.2 Pregnancies in Female Partners of Male Patients

Male patients will be instructed through the Informed Consent Form to immediately inform the investigator if their partner becomes pregnant during the study or until the last study visit. *A paper Clinical Trial Pregnancy Reporting Form should be completed and submitted to the Sponsor or its designee immediately (i.e., no more than 24 hours after learning of the pregnancy) either by faxing or by scanning and emailing the form with use of the fax number or e-mail address provided to investigators.* Attempts should be made to collect and report details of the course and outcome of any pregnancy in the partner of a male patient exposed to study drug. The pregnant partner will need to sign an Authorization for Use and Disclosure of Pregnancy Health Information to allow for follow-up on her pregnancy. *After the authorization has been signed, the investigator will submit a paper Clinical Trial Pregnancy Reporting Form when updated information on the course and outcome of the pregnancy becomes available.* An investigator who is contacted by the male patient or his pregnant partner may provide information on the risks of the pregnancy and the possible effects on the fetus, to support an informed decision in cooperation with the treating physician and/or obstetrician.

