- ^k Adverse events will be recorded starting on Day 1 after the study treatment injection through the last study visit. At the time of study enrollment, if the patient has any ongoing adverse events from Study CFD4870g, these events will also be entered into the extension study eCRF. Adverse events assessed by the physician as related to study drug should be followed until the event resolves or the event is assessed as irreversible, chronic, or stable, even if the patient's participation in the study has been terminated.
- ^l Record all concurrent ocular procedures performed on the study or non-study eye.
- ^m Subsequent to the initial treatment visit, patients treated with study drug will receive a telephone call 7 (± 2) days after each treatment visit to solicit adverse events.

Appendix 1

Schedule of Assessments (cont.)

Appendix 1-C: Schedule of Assessments for Patients Enrolled from Study CFD4870g: Months 67–96 and Early Termination

	Visit Month ^a										ET, ^b
	67–71	72	73–77	78	79–83	84	85–89	90	91–95	96	
Assessment windows (days) between monthly visits	±7	±7	±7	±7	±7	±7	±7	±7	±7	±7	≥30
Site to contact IxRS (as applicable) ^b	x	x	x	x	x	x	x	x	x	x	
Physical examination											x
Vital signs ^c											x
Central laboratory samples (hematology, coagulation, serum chemistry, urinalysis) ^d											x
Urine pregnancy test (if applicable) ^d	x	x	x	x	x	x	x	x	x	x	
Serum sample for anti-lampalizumab antibody and corresponding drug concentration ^d										x	x
Optional single whole-blood sample for genotyping ^d	Collect 1 sample at any timepoint from study patients at German site										
Patient-reported weight and height	Collect patient-reported weight and height once during the study										
BCVA testing (starting at 4 pm) ^e	x	x	x	x	x	x	x	x	x	x	

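### Non-serious AEs, SAEs judged unrelated and new pregnancies are collected only to the last visit, which for completers has no minimum interval after the last injection and can precede the protocol's own post-dose contraception windows

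*Combined protocol and SAP*

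**What the plan says.** **Visit timing.** Section 4.6.3 states: "The study scheduled visits should occur every 30 (± 7) days relative to the Day 1 visit date". Section 4.6 gives the same rule: "Study visits will be scheduled every 30" (±7) days, counted from Day 1. The schedules in Appendix 1 label the same ±7 days differently: "Assessment windows (days) between monthly visits".

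**Last injection.** In Table 1 (Section 3.1.3), patients from CFD4870g in the monthly arm "continue to receive monthly lampalizumab treatment (Months 1–95) without change". Patients from GX29455 are dosed through Month 53. No drug is given at the final visit, Month 96 or 54. The 23-day minimum in Sections 3.1.3 and 4.6.3 applies from dose to dose. Section 3.1.3 also allows a dose to be given up to 3 working days after its visit when an unexpected issue arises.

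**Early leavers.** Section 4.6.4 says of patients who withdraw early: "these patients should complete the ET visit assessments ≥ 30 days following the last study treatment". Section 4.6.5 applies the same interval to those who stop treatment and gives AE monitoring as a purpose. No upper limit is set.

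**End of reporting.** Section 5.3.1: "After initiation of study drug, all adverse events will be reported until the last study visit". After that, Sections 5.3.1 and 5.5 keep SAEs believed related to study drug reportable. The Appendix 1 footnotes require related AEs to be followed to resolution or stability even after participation ends.

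**Pregnancy.** Section 4.1.2.1 requires contraception for at least 30 days after the last dose in women and, in men, "for at least 30 days plus 90 days (a spermatogenesis cycle) after the last dose of study drug". Section 5.3.6.2 asks male patients to tell the investigator "if their partner becomes pregnant during the study or until the last study visit". Section 5.3.6.1 sets the same end point for female patients.

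**The concern.** The protocol sets a 30-day minimum after the last treatment for patients who leave early but sets none for patients who complete. The 23-day rule does not supply one, because no dose is given at the final visit. A completer whose final visit falls early therefore has a shorter tail of AE collection after the last injection than the protocol itself asks for at the ET visit.

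Two kinds of information are at stake. The first is later events after the final injection that are non-serious, or serious but judged unrelated: once the final visit has passed, no rule calls for their collection. The second is pregnancy. The protocol asks patients to avoid conception for a stated period after the last dose, but stops asking to hear of pregnancies before that period ends. For men this happens to every completer dosed on schedule.

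**Working it through.** **Inputs.** Visits every 30 days, ±7 (4.6, 4.6.3). Last dose at Month 95 or 53, final visit at Month 96 or 54 with no dose (Table 1). Dose delay of up to 3 working days (3.1.3). ET visit at ≥30 days (4.6, 4.6.4, 4.6.5). Contraception windows of 30 days and 30 + 90 = 120 days (4.1.2.1).

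**Check of the plan's own figures.** Day 1 plus Months 1–95 gives 1 + 95 = 96 injections. Day 1 plus Months 1–53 gives 1 + 53 = 54. Both match the stated maxima, so the last dose falls one visit before the final visit.

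**Gap from last dose to final visit, window counted from Day 1.** Let a be the deviation of the last dosing visit and b that of the final visit, each from −7 to +7. Gap = 30 + (b − a).
- Minimum: 30 − 7 − 7 = 16 days. Nominal: 30. Maximum: 30 + 7 + 7 = 44.
- Of the 15 × 15 = 225 day pairs, those below 30 days have b < a: 15 × 14 / 2 = 105 (47%).
- Those below 23 days have a − b of 8 to 14: 7 + 6 + 5 + 4 + 3 + 2 + 1 = 28 (12%).

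These are shares of possible day pairs. They would be shares of patients only if visits fell independently and uniformly in their windows, which the documents do not say.

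**Gap if the ±7 is read as visit to visit.** 30 − 7 = 23 to 30 + 7 = 37 days. Nothing falls below 23.

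**With a delayed last dose.** Three working days are 3 to 5 calendar days, depending on the weekday and ignoring public holidays. The minimum becomes 16 − 3 = 13 to 16 − 5 = 11 days (Day 1 anchor), or 23 − 3 = 20 to 23 − 5 = 18 days (visit to visit).

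**Against the 30-day interval (the ET floor and the window for women).**
- Day 1 anchor: shortfall of up to 30 − 16 = 14 days.
- Visit to visit: up to 30 − 23 = 7 days.
- At the nominal gap of 30 days: none.

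**Against the 120-day window for men.**
- Day 1 anchor: 120 − 44 = 76 to 120 − 16 = 104 days short.
- Visit to visit: 120 − 37 = 83 to 120 − 23 = 97 days short.
- Early leavers seen at day 30: 120 − 30 = 90 days short; less if the ET visit is later.

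**Scale against total follow-up.** 14 / (96 × 30) = 14 / 2,880 = 0.5% for CFD4870g patients. 14 / (54 × 30) = 14 / 1,620 = 0.9% for GX29455 patients.

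**The case against.** The best defence is that little is lost. The shortfall follows one of up to 96 or 54 injections. A call at 7 (±2) days after each injection asks about ocular symptoms, and the final visit includes slit-lamp examination and ophthalmoscopy. Table 4 treats an event as related unless another cause or implausible timing is shown, which widens what stays reportable. There is no control group, no formal sample size and no planned comparison of completers with early leavers. All of this stands, and it keeps the point minor. It does not remove the uneven floor or the pregnancy mismatch.

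A reader might also infer more than the documents support:
- **That all safety reporting stops at the last visit.** It does not. Related SAEs stay reportable, related AEs are followed, and Section 5.4.1 follows reported pregnancies to outcome.
- **That follow-up falls short of the protocol's AE risk windows.** The protocol defines no post-dose AE risk window. The 30-day and 120-day periods are contraception requirements, and the men's figure rests on a spermatogenesis cycle. They bear on pregnancy notification, not on how long AEs should be followed.
- **That early leavers always have longer follow-up than completers.** Patients who stop treatment are asked to return, and under Section 4.7 those who withdraw consent are not followed at all.
- **That 16 days is the floor.** It depends on the Day 1 anchor. The schedule label allows 23, and a delayed dose allows less than either.
- **That Section 4.12.1 needs a common on-treatment AE cut-off.** This is an analysis preference. No planned comparison would change without it.

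**Conclusion.** The point holds as a minor inconsistency in safety capture. Completers have no stated minimum interval between last injection and final visit. The gap can be as short as 16 days (Day 1 anchor) or 23 days (visit to visit), and shorter with a permitted dose delay, whereas the ET visit is set at 30 days or more. What is lost is limited to non-serious AEs, SAEs judged unrelated, and new pregnancies.

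The pregnancy mismatch is the firmer half. For women the shortfall is possible but not systematic, since the nominal gap equals the 30-day window. For men it occurs under either reading of the visit window.

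The effect on cumulative AE incidence over 54 to 96 months is very small. I assume that few pregnancies will arise, given the age of a population with geographic atrophy; the documents give no count. The 76-to-104-day figure assumes the Day 1 anchor and a last dose given on schedule, because a missed or delayed dose would shift it.

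**What to change.** - Reconcile Sections 5.3.6.1 and 5.3.6.2 with the post-dose windows in Section 4.1.2.1, so that pregnancy notification covers the same period as the contraception requirement for each sex.
- Reconcile Sections 4.6, 4.6.4 and 5.3.1 so that completers have the same minimum AE-reporting interval after the last injection as the ET visit already carries. If the final visit falls earlier, a telephone contact at the end of the interval is enough.
- State one anchor for the ±7 days, and make Sections 4.6 and 4.6.3 agree with the label in the Appendix 1 schedules.

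A common AE cut-off in Section 4.12.1 is optional.

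The cost is protocol wording, a longer pregnancy-notification period (mainly for men), and at most one telephone contact per affected completer. No extra clinic visit is needed.
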